Edition Number: **4**

Date: **11 February 2022**

- To evaluate the efficacy of sirolimus followed by durvalumab as neoadjuvant treatment for Stage I, II, and IIIA NSCLC

Secondary Objective(s):

- To evaluate the efficacy of sirolimus followed by durvalumab as neoadjuvant treatment for Stage I, II, and IIIA NSCLC
- To evaluate response to sirolimus followed by durvalumab in patients with PD-L1 positive vs. PD-L1-negative tumors
- To evaluate the association between blood mutation burden and response to sirolimus followed by durvalumab

Exploratory Objective(s):

- To evaluate the immune-mediated effects of sirolimus followed by durvalumab
- To investigate tumor and immune microenvironment changes in tissue samples

Study Design:

Up to 31 patients with NSCLC will be enrolled in this study at Emory University Winship Cancer Institute and associated clinical sites. Eligible patients will complete 3 weeks of daily oral sirolimus followed by 2 cycles of durvalumab treatment prior to proceeding to standard of care surgical resection. Durvalumab will be administered at a dose of 1500mg Q 3 weeks starting on C1D1 for up to 2 cycles that are 21 days in length. Pharmacodynamic analysis will be done using PD samples collected at baseline (tissue) and with blood samples on day 1, day 22 C1 prior to durvalumab, day 43 C2 durvalumab, and at the time of surgery (blood and tissue). Additional post surgery blood samples will be collected at 1-, 3-, and 6-months post-surgery. See Appendix D for schedule of Biomarker collection. Patients will proceed to surgery within a 2–3-week period post 2nd dose of durvalumab but not earlier than two weeks after the administration of durvalumab i.e. not earlier than C2D14. Additionally, as an optional study, patients will self-administer heavy water (D2O) 50ml orally three times a day from day 22 C1 through day 27 followed by 50ml orally twice a day through the day prior to surgery in order to label dividing cells for research tracking purposes.

Number of Centers: Emory University Winship Cancer Institute and affiliated hospitals

Number of Patients: 31

Study Population: Resectable Stage 1-3A NSCLC

Inclusion Criteria:

- Pathologically documented NSCLC who are candidates for surgical resection
- Capable of signing informed consent

- Age \geq 18 years at time of study entry.
- Eastern Cooperative Oncology Group (ECOG) performance status of 0 or 1
- Life expectancy of \geq 26 weeks
- Body weight >30 kg

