^g If TSH is measured within 14 days prior to Day 1 (first infusion day), it does not need to be repeated at day 1.

^h Free T4 may only be measured if TSH is abnormal or if there is clinical suspicion of an AE related to the endocrine system.

Clinical Study Protocol

Drug Substance Sirolimus (Rapamune)

Study Number **19-20015**

Edition Number: **4**

Date: **11 February 2022**

- ⁱ For women of childbearing potential only. A urine or serum pregnancy test is acceptable. Women of childbearing potential are required to have a pregnancy test within 7 days prior to the first dose of study drug. Pregnancy test may occur on Day 1, but results must be available and reviewed by the treating physician or Investigator prior to commencing an infusion
- ^j For AEs/SAEs reported during screening, additional information such as medical history and concomitant medications may be needed
- ^k Results for LFTs, electrolytes, full blood count and creatinine must be available before commencing an infusion (within 3 days) and reviewed by the treating physician or Investigator prior to dosing.
- ^l RECIST assessments will be performed on images from CT (preferred) or MRI, each preferably with IV contrast of the chest, abdomen (including liver and adrenal glands) and pelvis. Pelvic imaging is recommended only when primary or metastatic disease in the pelvic region is likely. Additional anatomy should be imaged based on signs and symptoms of individual patients at baseline and follow-up. Baseline assessments should be performed no more than 28 days before the date of randomization and, ideally, should be performed as close as possible to and prior to the start of IP. Repeat assessments will be performed as close as possible to surgery date.
- ^m Peripheral blood collection for biomarker analysis will be obtained at 3- and 6-months post-surgery
- ⁿ Screening/Baseline Cross-sectional Imaging (CT, PET, or MRI) for RECIST should be within 6 weeks of starting C1D1 of trial therapy

Note: All assessments on treatment days are to be performed prior to infusion, unless otherwise indicated.

C Cycle; ECG Electrocardiogram; IM Intramuscular; LFT Liver function test; T₄ Thyroxine; TSH Thyroid-stimulating hormone.

Clinical Study Protocol

Investigational Drug Substance: MEDI4736 Sirolimus (Rapamune)

Study Number **19-20015**

Edition Number: 4

Date: **11 February 2022**

TABLE OF CONTENTS

PAGE

PROTOCOL SYNOPSIS	2
SCHEDULE OF STUDY ASSESSMENTS	8
TABLE OF CONTENTS	12

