2. STUDY OBJECTIVES

2.1 Co-Primary objective(s)

- To evaluate the safety and tolerability of sirolimus followed by durvalumab as neoadjuvant treatment by incidence of adverse events, with severity per NCI CTCAE v5.0.
- To evaluate the efficacy of sirolimus followed by durvalumab as neoadjuvant treatment for Stage I, II, and IIIA NSCLC by complete pathologic response at surgical resection scored by a pathologist.

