3. STUDY DESIGN

3.1 Overview of study design

This is a Phase Ib open-label, single-arm study in newly diagnosed stage I-IIIA NSCLC patients, to test sirolimus in combination with durvalumab as neoadjuvant treatment prior to curative-intent surgical resection. The safety and tolerability as well as efficacy of combination sirolimus with durvalumab will be evaluated in this treatment setting. The study is also designed to investigate a number of laboratory correlative studies to define mechanisms of anti-tumor activity of sirolimus + durvalumab and several potential predictive biomarkers, which will help identify patients who are more likely to respond to treatment. Finally, the study will also include DFS and OS as secondary endpoints.

Up to 31 patients with NSCLC will be enrolled in this study at Emory University Winship Cancer Institute and affiliated sites. Enrollment will occur in 2 parts based on Simon 2 stage design, in which at least 2 of the first 16 patients must achieve pathologic complete response in order for the study to enroll 15 additional patients.

Eligible patients will complete 2 cycles of outpatient study treatment prior to proceeding to standard of care surgical resection. In order to allow a reliable assessment of the contribution of sirolimus versus durvalumab to the observed clinical and PD outcome, treatment will start with sirolimus 6mg orally for one loading dose followed by 2mg orally once daily three weeks prior to the start of durvalumab. Durvalumab will be administered at a dose of 1500mg Q 3 weeks starting on C1D1 for up to 2 cycles that are 21 days in length. Pharmacodynamic analysis will be done using PD samples collected at baseline (tissue) and with blood samples on day -7, C1D1 prior to durvalumab, C1D8, C2D1, C2D8 and at the time of surgery (blood and tissue). Additional post surgery blood samples will be collected at 1, 3, and 6 months post-surgery. See **study schedule of assessments** for schedule of Biomarker collection. Patients will proceed to surgery within a 4-week period post 2nd dose of durvalumab but not earlier than one week after the administration of durvalumab i.e. not earlier than C2D8. Additionally, patients will self-administer heavy water (D2O) 50ml orally three times a day from C1D1 through C1D5 followed by 50ml orally twice a day through the day prior to surgery in order to label dividing cells for research tracking purposes.

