The dose of sirolimus chosen for this study is based on our pre-clinical data that indicate that a lower dose is most likely to result in the desirable pharmacodynamics effects on the immune system. For clinical use in the renal transplant setting and high immunologic risk transplants, sirolimus is recommended at an initial loading dose of 15 mg followed by 5mg/day maintenance, with adjustments based on trough level. In lymphangiomyomatosis (LAM), the recommended dose is 2 mg daily to block mTOR pathway activation; median whole blood

Date: **11 February 2022**

sirolimus trough concentration after 3 weeks of receiving sirolimus tablets at a dose of 2 mg/day was 6.8 ng/mL (interquartile range 4.6 to 9.0 ng/mL; n = 37). As the sirolimus treatment phase will be only 3 weeks, a single loading dose of 6mg on day 1 will be followed by 2mg daily. No dose changes will be made for individual patients given this short term low dose regimen designed to reach levels of 5-15 ng/ml, which was noted in pre-clinical studies to correlate with proliferation of memory T cells. This lower dose is also likely to be tolerated better by patients.

As an added safety measure, the first 6 patients will be monitored through hospital discharge following surgical resection to assess for dose limiting toxicities (DLTs) related to sirolimus followed by durvalumab therapy. DLTs and safety analysis are described in section 6.4.

Patients will be closely monitored for safety and tolerability throughout the study. Safety assessments will include collection and monitoring of adverse events and laboratory abnormalities graded per the National Cancer Institute Common Terminology Criteria for Adverse Events, Version 5.0 (NCI CTCAE v5.0). Tumor tissue samples, normal lung parenchyma, whole blood samples, and optional lymph node samples will be collected for biomarker assessments.

After study treatment discontinuation, patients will be followed per SOC, but information on recurrence and survival will be collected every 6 months for up to 2 years after the last patient receives the last dose in the study (in person or by phone). Patients who discontinue the study due to adverse events will be followed until resolution or stabilization of the adverse event. Appropriate dose modifications are described in Section 6. No investigational or commercial agents or therapies other than those described below may be administered with the intent to treat the patient's malignancy.

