11.3 Determination of sample size

Pathologic complete response is rare following neoadjuvant chemotherapy but was reported in 0-8% of cases³⁹. The current study is designed to test improved rate of pathologic complete response from 10% to 25% treatment with sirolimus followed by durvalumab. Using a MinMax 2-stage design, a total of 31 patients will be enrolled in 2 stages. At the end of stage I, at least 2 of 16 patients must achieve complete pathologic complete response in order for the study to enroll 15 additional patients. The regimen of sirolimus followed by durvalumab will be considered to have sufficient efficacy to warrant further testing in this patient population if 6 or more of the 31 patients achieve a pathologic CR at the end of stage II. The study has 80% power at a 1-sided alpha of 0.1 to show a compelling 25% pCR compared to a less compelling rate of 10%. Because this is a signal finding study, an alpha of 0.1 is considered reasonable since any promising signal will be confirmed in a larger follow-up study.

Planned total number of patients is 31 over 2 years, with an estimated accrual rate of approximately 1-2 patients/month. Racial, ethnic, and gender accrual estimates below are based on 2010 Atlanta Census demographic information.

Accrual Targets			
Ethnic Category	Sex/Gender		
	Females	Males	Total
Hispanic or Latino	1	+ 1	= 2
Not Hispanic or Latino	14	+ 14	= 28
Ethnic Category: Total of all subjects	15 (A1)	+ 15 (B1)	= 30 (C1)
Racial Category			
American Indian or Alaskan Native	0	+ 0	= 0
Asian	1	+ 1	= 2
Black or African American	6	+ 6	= 12

Clinical Study Protocol

Investigational Drug Substance: MEDI4736 Sirolimus (Rapamune)

Study Number **19-20015**

Edition Number: 4

Date: **11 February 2022**

Native Hawaiian or other Pacific Islander	1	+	1	=	2
White	7	+	7	=	14
Racial Category: Total of all subjects	15	(A2)	15	(B2)	30 (C2)
(A1 = A2)		(B1 = B2)		(C1 = C2)	

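### The sirolimus lead-in cannot separate the two drugs' contributions to efficacy as Section 3.1 says, and the blood baseline that its pharmacodynamic part needs is not fixed before the first sirolimus dose

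*Combined protocol and SAP*

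**What the plan says.** Section 3.1 starts treatment with three weeks of sirolimus and gives the reason: "In order to allow a reliable assessment of the contribution of sirolimus versus durvalumab to the observed clinical and PD outcome". The same section opens: "This is a Phase Ib open-label, single-arm study in newly diagnosed stage I-IIIA NSCLC patients". Section 2.1 measures the efficacy co-primary objective "by complete pathologic response at surgical resection scored by a pathologist". The Schedule of Study Assessments places tumour imaging at screening and before surgery. Section 3.1 takes pharmacodynamic (PD) tissue at baseline and at surgery.

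Section 11.3 tests 10% against 25% pCR. The only background rate it gives is this: "Pathologic complete response is rare following neoadjuvant chemotherapy but was reported in 0-8% of cases".

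For PD blood, Section 3.1 lists "blood samples on day -7, C1D1 prior to durvalumab", followed by draws counted in durvalumab cycle days. The synopsis instead begins "with blood samples on day 1, day 22 C1 prior to durvalumab". The schedule puts the first research blood in the sirolimus column, headed days 1-21, and its closing note reads: "All assessments on treatment days are to be performed prior to infusion, unless otherwise indicated".

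**The concern.** A lead-in separates two drugs only for outcomes that are measured at the boundary between them. Neither pCR nor RECIST is measured there, so for efficacy Section 3.1 claims a property that the design does not have. The risk is that a trial meeting its success rule is read as showing that sirolimus contributed, when durvalumab alone may explain the result.

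Blood markers are measured at the boundary, so the PD half of the claim can be partly met. That depends on a baseline drawn before sirolimus. If some patients are first bled on the drug, the sirolimus-only change is understated or absent for them and cannot be recovered later.

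**Working it through.** **1. The plan's own figure.** Inputs from Section 11.3: continue with at least 2 of 16 pCRs, success with at least 6 of 31, rates 10% and 25%.

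P(success | p) = sum over x = 2 to 16 of P(X1 = x) × P(X2 ≥ 6 − x), with X1 ~ Bin(16, p) and X2 ~ Bin(15, p).

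At p = 0.25 this gives 0.805; at p = 0.10 it gives 0.079. The stated 80% power and one-sided alpha of 0.1 reproduce. The sample size is not at fault.

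**2. What is read at the change of drug (day 21 to day 22).**

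| Outcome | When read | Read between the drugs? |
|---|---|---|
| pCR | at resection | no |
| RECIST response | screening, before surgery | no |
| Tissue PD | baseline, surgery | no |
| Blood PD | first draw, then day 22 before durvalumab, then later | yes |
| Adverse events | from consent (Section 10.4) | yes, days 1-21 |

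No concurrent arm fills the gap, and neither does an external rate. Section 11.3 cites chemotherapy. For PD-1/PD-L1 blockade alone, Section 1.1.1 gives major pathologic response rates (45% and 21%, other drugs) and no pCR rate.

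**3. What the success rule can distinguish.** Use the formula in step 1, suppose that sirolimus adds nothing, and let p be the durvalumab-alone pCR rate. The values of p are assumptions. All 31 patients are taken as evaluable.

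| Assumed durvalumab-alone pCR | P(success rule met) |
|---|---|
| 8% | 0.032 |
| 10% | 0.079 |
| 12% | 0.152 |
| 15% | 0.303 |
| 20% | 0.587 |
| 25% | 0.805 |

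**4. Where day -7 falls.** Sirolimus runs on days 1-21 (Section 5.2.2), and durvalumab C1D1 is day 22 (Section 8.2.3, sirolimus level).

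- Counted back from C1D1: 22 − 7 = study day 15, or day 14 if a day 0 is counted. Either day is on sirolimus. With the 62-hour half-life in Section 1.6.2.2 and ignoring the loading dose, the level on day 15 is 1 − 0.5^(14 × 24/62) = 0.977 of steady state.
- Counted back from the first sirolimus dose: before treatment.

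Section 3.1 does not say which. Its other treatment-phase draws are counted from durvalumab, and schedule footnotes f and g call Day 1 the first infusion day. Table 1 and the synopsis use day 1 for the first sirolimus dose. Section 8.1.1 counts screening back from Day -7, which fits a pre-treatment day: on the day-15 reading, the screening window would run into the sirolimus period.

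**5. Whether a day 1 draw settles it.** Not as written. Sirolimus is an oral morning dose (synopsis; Section 5.2.3) and no infusion takes place on day 1, so a rule tied to the infusion does not order the draw against the first dose. The day 22 draw is explicitly placed before durvalumab, and Section 8.2.5.1 explicitly places fresh biopsies before any study treatment. The day 1 blood has no matching words.

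The number of draws also differs. Section 3.1 lists nine (day -7, C1D1, C1D8, C2D1, C2D8, surgery, months 1, 3 and 6), matching the nine research samples in Table 10. The synopsis lists seven.

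**6. Sirolimus level.** One sample is planned (Table 10), on day 22 in Section 8.2.3 but day 23 in Section 8.1.2. The last dose is on day 21. One extra day multiplies the level by 0.5^(24/62) = 0.765, about 24% lower.

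**The case against.** The strongest reply is that the sentence does little harm. Section 11.2.2 limits the conclusion to the response rate when sirolimus is followed by durvalumab, and Section 11.3 applies the rule to the regimen and leaves confirmation to a larger study. This stands. A reader might infer that the plan's decision rule claims a sirolimus effect; it does not. The over-claim is confined to Section 3.1.

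Second, clinical outcome includes safety. Patients are evaluable for toxicity from the first sirolimus dose (Section 9.1.2), and events on days 1-21 precede any durvalumab. This also stands, so the sentence should be narrowed and not deleted. The dose-limiting toxicity window opens only at durvalumab (Section 6.3), so the attribution rests on the general adverse event data.

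Third, Day -7 is probably pre-treatment. Section 8.1.1 favours that, and Section 1.5.1.2 lists baseline blood apart from draws during treatment. A reader might infer that the baseline is lost; the documents show only that it is not fixed. Even on the day-15 reading, the day 22 draw still gives a pre-durvalumab reference. Later change from it is not purely durvalumab, because about 12% of the sirolimus level remains at C1D8: 0.5^(8 × 24/62) = 0.117.

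Fourth, a reader might infer from Section 3.1 that under-exposure erodes power, since the regimen is "designed to reach levels of 5-15 ng/ml" while the trough data quoted there (median 6.8 ng/mL, interquartile range 4.6 to 9.0) have a lower quartile below 5. The documents do not support this. Those data come from 37 patients with another disease, no threshold links sirolimus level to pCR, and the 25% alternative is for the regimen as given.

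**Conclusion.** The point holds in a limited form. For pCR, RECIST and tissue PD, the lead-in cannot apportion effect between the drugs, and this follows from the design without any assumption. The probabilities of 7.9%, 30.3% and 58.7% only illustrate it and rest on assumed durvalumab-alone rates.

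For blood PD the aim can be met as a within-patient before-and-after change, provided that the baseline precedes sirolimus. The passages conflict and none guarantees it. No section names the baseline-to-day-22 contrast as an analysis, although the list in Section 11.2.3 is open-ended, so the accurate statement is that none is specified.

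None of this calls for a control arm, a different sample size or a different decision rule. Nor is a comparison of major pathologic response with the cited 45% and 21% needed: it would be another cross-study comparison, with other drugs and an endpoint for which the protocol states no cut-off. The point should be fixed, at low cost, and does not threaten the primary test.

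**What to change.** 1. In Section 3.1, limit the sentence to blood PD change and early toxicity on sirolimus. State there or in Section 11.3 that pCR and RECIST describe the sequence as a whole, and that reaching 6 of 31 does not show that sirolimus adds to durvalumab.
2. Reconcile the synopsis, the schedule with its footnotes and note, Section 3.1 and Section 8.1.1 on the meaning of Day 1 and Day -7, so that the baseline research blood is drawn before the first sirolimus dose. Bring the list of research draws into agreement with Table 10 at the same time.
3. In Section 11.2.3, name the change from that baseline to the pre-durvalumab day 22 draw as the sirolimus-only PD comparison.
4. Reconcile the day of the sirolimus trough sample between Sections 8.1.2 and 8.2.3. Any summary of the level is optional and descriptive.

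The cost is an amendment to wording and instructions to sites on the order of the first blood draw. No extra patient, assay or dose change is needed. The price is a narrower claim for the lead-in. If patients have already been treated, recorded draw and dose times would show whose baseline qualifies.

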3.2 Study schema

Figure 1. Study Schema

Durva: 1500mg of durvalumab

W: week; M: month; SOC: standard of care; Tx: treatment

3.3 Surgical Resection

Following neoadjuvant systemic treatment described above, patients will undergo surgical resection of the primary tumor and associated lymph nodes. Repeat chest CT scan and/or PET/CT scan will be obtained prior to surgical resection. Resection may be accomplished via an open or minimally invasive procedure (i.e., thoracotomy, sternotomy, video assisted thoracic surgery (VATS) or robotically assisted VATS.)

Anatomic resection via segmentectomy, lobectomy, bilobectomy or pneumonectomy is strongly preferred although wedge resection is acceptable for very small (2 cm or less) tumors located peripherally where wedge resection permits a wide margin (at least 1 cm in all directions).

Hilar and mediastinal lymph node dissection or sampling should be performed whenever possible. For right sided resections, the recommended sampling includes lymph nodes from levels 4R, 7, 10R, and 11R. For left sided resections, the recommended sampling includes lymph nodes from levels 5/6, 7, 10L, and 11L.

Pathologic specimens will undergo standard histopathologic and immunohistochemical evaluation for lung cancer. Sections of tumor and normal tissue specimens will be fresh frozen and formalin-fixed for correlative studies. Sections of lymph nodes will be freshly prepared in media and formalin-fixed for correlative studies. Whole blood samples will be collected at the time of surgical resection for correlative studies. The blood will be processed for PBMC, plasma, and serum for correlative studies.

At the postoperative follow-up visit, patients whose tumors have not demonstrated evidence of pathologic response and who have radiographic progression will have an end-of-study treatment visit, after which they will be followed per SOC, as deemed clinically appropriate. Whole blood will be collected at postoperative follow-up visit and will be processed for plasma, serum, and PBMC for correlative studies.

3.4 Study oversight for safety evaluation

There will be a planned safety assessment of the first 6 patients, who will be monitored through hospital discharge following surgical resection to assess for dose limiting toxicities (DLTs) related to sirolimus followed by durvalumab therapy. If $\geq 2/6$ patients have a DLT then additional enrollment will be halted until safety assessment is completed.

